4.2. Adherence and protocol deviations

Non-adherence to protocol procedure assessments according to *Figure 1* (SPIRIT diagram) are considered as protocol deviations and will be reported accordingly.

	Enrolment	Follow-up	End	points
TIMEPOINT	0	Individual schedule	12 months	24 months
			**	***
ENROLMENT:				
Eligibility screen	Х			
Informed consent	Х			
INTERVENTIONS:				
Standard of care (control)	x-		X	
VITAL model of care	X-		x	
ASSESSMENTS:				
Screening	X			
Socio-demographic data / clinical history Socio-demographic data ART history Comedication Family planning/sexual health Adherence to ART Health preferences* Availability of cell-phone(s) and number(s) Type, time and weekday of eHealth support	x	х		
Pharmacy refill (from ART card) Number of ART / TB / TPT pills dispensed and next refill date	х	х		
Clinical assessment Serious illness / hospitalization since last visit Pregnancy / breastfeeding Next VL due date ART action taken / TPT action taken Adherence to ART (if VL unsuppressed)* Type of EAC (if VL unsuppressed)* ART changes	х	х		
Mental health assessment • AUDIT-C, PT-PTSD, PHQ-9, GAD7, Druguse	х	Х		
Viral load database review Viral load results and dates Treatment changes	х	х	х	х
Qualitative in-depth interview with a subset of participants		х		

Figure 1. SPIRIT figure for the schedule of enrolment, interventions, and assessments. The color code corresponds to the responsible person for the assessment or task: Brown: VITAL study team, blue: clinic staff, green: VITAL data management team, purple: other VITAL study team members.

TB: tuberculosis; TPT: tuberculosis preventive therapy; VL: viral load; EAC: enhanced adherence counselling; * in VITAL intervention clinics only; ** 12 months window; *** 24 months window: 16-18 months

4.3. Analysis populations

The VITAL trial asses a model of HIV care in a "real-world" setting. The main interest is to assess effectiveness of the VITAL intervention, i.e. the degree of effect under "real-world" conditions. Accordingly, the ITT population is the analysis population of most relevance. Therefore, in the primary analysis, we will analyse participant outcomes in the cluster they were enrolled in, independent of their follow-up. As a sensitivity analysis we will conduct a per-protocol analysis

includes participants for whom the VITAL intervention was technically successful defined as all viral loads available in the VITALapp \leq 31 days after phlebotomy.

5. Trial population

5.1. Screening data

No specific screening data were captured, aside from those used to determine eligibility for the trial (see 5.2).

5.2. Eligibility

Full inclusion/exclusion criteria are as follows:

At **individual level**, inclusion criteria at enrolment for the VITAL trial are the following:

- taking ART;
- ≥ 18 years old;
- provided written informed consent;
- expressed the intention to remain at the same facility for the duration of the trial at enrollment; and
- not enrolled in another study judged as non-compatible by the (local) principal investigator.

At **cluster level**, the inclusion criteria for the VITAL trial are the following:

- nurse-led public or missionary clinic in the districts of Butha-Buthe and Mokhotlong;
- consent of clinic management (signed agreement with clinic management);
- access to the internet (internet connection must not be constant, but there must be possibility to down- and upload information daily); and
- the clinic sends plasma VL samples to Butha-Buthe government hospital laboratory for analysis.

Screening/eligibility data will be summarized in a CONSORT flowchart, showing the total number of clusters screened and the reasons for screening failures.

5.3. Recruitment

The CONSORT flowchart will display the numbers of clusters randomized by group. Further, the flowchart will include the numbers of participants screened and enrolled per cluster.

5.4. Withdrawal/follow-up

The CONSORT flowchart will summarize disengagement from care as well as reason for it (dead, hospitalized, transfer-out, stopped ART no information found after tracing) and study withdrawal, by group.

5.5. Baseline participant characteristics

Baseline participant characteristics will be summarized by group, using medians and interquartile ranges for continuous variables and numbers and percentages for categorical variables. There will be no formal testing for baseline characteristics differences across randomized groups (9,10).

6. Analysis

Analyses will follow CONSORT guidelines, including extensions for non-inferiority trials (11,12). Analyses will include all follow-up to the date of data freeze; as well as documented and reasoned changes thereafter.

6.1. Outcome definitions

An overview of the primary and all secondary endpoints is given in *Table 3*. For the primary endpoint, two hypotheses will be hierarchically tested:

- 1. non-inferiority in the ITT population; and
- 2. superiority in the ITT population.

Since the first approved protocol version and registration of the trial, the following amendments were made to the outcomes:

Change to the primary endpoint:

- In line with the national HIV treatment guideline of Lesotho update in 2022 and considering the detection threshold of 40 copies/mL of the increasingly used point-of-care viral load testing, the cutoff for viral suppression was raised from 20 copies/mL to 50 copies/mL.

Changes to secondary endpoints:

- In all secondary endpoints the cutoff of viral suppression was adapted to 50 copies/mL as for the primary endpoint.
- "Switch" considered as change of ART core agent was replaced by "ART regimen modification" since the nation-wide roll-out of dolutegravir in Lesotho led to a change of the guidelines when to switch to second-line due to ART failure and core agent changes became extremely rare among persons taking dolutegravir.
- In secondary endpoint 13, we changed "having received a course of TPT throughout the study" to "having ever received a course of TPT," as our first TPT measurement was not consistently collected at enrolment, making the baseline estimate problematic.

Secondary endpoints moved to different analyses/ manuscripts:

The following endpoints are unchanged but will be considered in separate analyses for separate manuscripts as they would go beyond the scope of the main manuscript.

- "Proportion of participants requesting a VL result notification through SMS in intervention clusters"
- "Proportion of SMS delivered successfully in intervention clusters"

- "Proportion of participants using the call-back option through District ART Nurse in intervention clusters"
- "Proportion of participants screened positive for TB by automated call in intervention clusters"

Dropped secondary endpoints:

- "Proportion of participants appreciating the automated differentiated service deliver model in intervention clusters" was replaced by qualitative in-depth interviews with a subset of participants (already conducted).
- "Proportion of health care providers appreciating the automated differentiated service delivery model" was dropped for feasibility.

Addition of sensitivity analyses:

- We added a sensitivity analysis for the primary endpoint using imputation for VLs missing at 24 months in the ITT population.
- We added a sensitivity analysis for the primary endpoint in a per-protocol population including participants for whom all viral loads were available in the VITALapp ≤31 days after phlebotomy.

Primary endpoint	Population	Comparison
Proportion of participants engaged in care	ITT	i. Non-inferiority
(defined as documented visit attendance) with documented viral suppression (< 50 copies/mL) 24 months (16-28 months) after enrollment*		ii. Superiority

Sensitivity analysis for the primary endpoint

1.	Proportion of participants engaged in care	ITT	13.:
	(defined as documented visit attendance)		i. Non-inferiority
	with documented viral suppression (<1000 copies/mL) 24 months (16-28 months) after enrollment		ii. Superiority

 Proportion of participants engaged in care (defined as documented visit attendance) with documented viral suppression (<50 copies/mL) 24 months (16-28 months) after enrollment ITT using imputation for VLs missing at 24 months

PP*

 Proportion of participants engaged in care (defined as documented visit attendance) with documented viral suppression (<50 copies/mL) 24 months (16-28 months) after enrollment

4.	Proportion of participants with viral re-	ITT	45. hierarchical (i.e. 4.
	suppression (< 50 copies/mL) 24 months (16-		only if the primary
	28 months) after enrollment among all		endpoint is non-inferior,
	participants with an unsuppressed VL (≥ 50		and 5. only if 4 is
	copies/mL) during the first 12 months of		superior):
	follow-up		Superiority
	•		, ,
5.	Proportion of participants with sustained	ITT	
	viral suppression (defined as >1 VL <50		
	copies/mL) during 24 months follow-up		
	ondary endpoints indicative of clinical		
ber 6.	nefit or harm Rate of mortality at 12 and 24 months after	ITT	67.: Equivalence
٠.	enrollment		8.: Superiority
			on superiority
7.	Proportion of participants with confirmed TB		
	diagnosis at 12 and 24 months after		
	enrollment		
8.	Disengagement from care at 12 and 24		
	months after enrollment		
	ondary endpoints expressing supportive		
	dence Time to follow-up VL in case of an	ITT	913.: Superiority (for 9
9.	unsuppressed VL (≥ 50 copies/mL)	111	11. the upper bound of
	unsuppressed vi (2 30 copies/inii)		the 95% CI must be below
10	Time to ART regimen adaption in case of		1, and for 1213. the
10.	virologic failure**		lower bound of the 95% C
	virologic failure		must be above 1)
11.	Rate of clinic visits at 24 months after		must be above 1,
	enrollment		
12.	Proportion of participants with ART regimen		
	modification due to virologic failure at 12		
	and 24 months among participants with		
	virologic failure**		
12	Proportion of participants having ever		
	opo. don or participants naving ever		

Table 3. Primary and secondary endpoints as well as sensitivity analyses. *The per-protocol analysis includes participants for whom all viral loads were available in the VITALapp ≤31 days after phlebotomy. **Virologic failure is defined according to the implementation in VITAL, i.e. two consecutive VLs ≥1'000 copies/mL or three consecutive VLs ≥20 copies/mL from VITAL start - 22.12.2022 and two consecutive VLs ≥50 copies/mL from 23.12.2022 – VITAL closure.

6.2. Analysis methods

General: Continuous variables will be inspected using histograms: 1) to assess for outliers which may be queried for accuracy, and 2) to assess whether appropriate transformations are required for the regression model. Outcomes will be summarized using medians and interquartile ranges for

continuous variables and numbers and percentages for categorical variables, by randomized group. Percentages will be reported to one decimal place. For the primary outcome and its sensitivity analyses, we will report adjusted odds ratios and adjusted risk differences derived from regression models. If a model fails to converge using the identity link function (for estimating the adjusted risk difference), only adjusted odds ratios will be reported. Methods for secondary analyses are detailed below; for secondary analyses aligned with the primary outcome analysis, we will report adjusted odds ratios. If the number of outcome events is insufficient to support reliable coefficient estimation (e.g., fewer than 10 events per parameter), no regression model will be fitted. We will consider the day of enrolment until the day of primary endpoint VL or until 28 months after enrolment if endpoint VL missing as study period for each participant.

Primary outcome: For the analysis of the primary outcome, we will use a multi-level logistic regression model including clinic cluster as a random effect, arm allocation and the randomization stratification factor (district) as a fixed effect. Unavailability of a viral load or only an invalid viral load result in the predefined primary endpoint window (for any reason) will be considered as failure. Results will be reported as adjusted odds ratios and absolute differences with confidence intervals. For the primary endpoint, non-inferiority in the ITT population and superiority in ITT will be assessed but no statistical multiplicity adjustment will be needed because of the closed testing principle. For the non-inferiority comparison, a confidence interval approach will be used. Under the assumptions of the sample size calculation, non-inferiority is compatible with the lower bound of the one-sided 97.5% confidence interval for the adjusted odds ratio for the primary outcome exceeding 0.8. A figure illustrating the confidence interval and the non-inferiority margin will be presented. If the non-inferiority is established, then we will assess for superiority by assessing whether the two-sided 95% confidence interval of the adjusted odds ratio excludes 1.

Assessment of cost (primary outcome): We will analyse cost-effectiveness if the intervention is found to be superior or assess the budget impact if the intervention is found to be non-inferior. For the cost-effectiveness analysis, we will use the primary endpoint and mathematical models of HIV transmission. Costing data will include: (1) conversion rate of local currency to U.S. dollars at 6-month intervals over the life of the project; (2) costs of all commodities used in the intervention; (3) average time clients spent with intervention including transportation, (4) staff time and representative salaries; (5) local average wages of the target population; (6) remunerations to clinics; and (7) other relevant costs, including training of providers and transport costs.

Time and motion studies are conducted to collect the costing data necessary to provide the intervention. All clinics contributed several time and motion observations. An experienced research assistant collects data on time required to complete each step of the intervention. Observing multiple visits allows estimation of the average time taken for each step. The time taken for research purposes (e.g. data collection) is noted separately from the estimated time needed for clinical services. In addition, interviews with study staff to quantify the effort required for each step of the intervention are conducted, as well as interviews with participants to assess opportunity costs. We also ask participants what expenses and opportunity costs they incurred while receiving the intervention. Furthermore, we collect data on the average cost of medical care in Lesotho associated with HIV infection and AIDS through literature review. A discount rate of 3% is used with sensitivity analysis of 0% to 5%.

Sensitivity analyses (primary outcome):

- Proportion of participants engaged in care (defined as documented visit attendance) with documented viral suppression (<1000 copies/mL) 24 months (16-28 months) after enrolment: The first sensitivity analysis assesses the robustness of the primary analysis to the primary endpoint definition by repeating the primary outcome analysis (ITT) with a VL cutoff modified to 1'000 copies/mL.
- 2. Proportion of participants engaged in care (defined as documented visit attendance) with documented viral suppression (<50 copies/mL) 24 months (16-28 months) after enrolment: The second sensitivity analysis assesses the robustness of the primary analysis to the primary endpoint definition by repeating the primary outcome analysis (ITT) with imputing the VLs of participants who were engaged in care but do not have a documented viral load at 24 months using the viral load history of the participants.
- 3. Proportion of participants engaged in care (defined as documented visit attendance) with documented viral suppression (<50 copies/mL) 24 months (16-28 months) after enrolment: The third sensitivity analysis assesses the robustness of the primary analysis to technical challenges with viral load result availability by repeating the primary outcome analysis in the per-protocol population defined as participants for whom all VL results were available in the VITALapp ≤31 days after phlebotomy during the study period.

Effect modification (primary outcome): For effect modification of the primary outcome the following variables will be considered:

- i. Age groups (18-24, 25-39, 40-59, and ≥60 years)
- ii. Gender (female, male)
- iii. Cell phone access (yes, no)

Analyses will be performed as for the main primary outcome analysis including an interaction term between these potential effect modifiers and the randomized group. If an interaction term is found to be significant (p-value<0.05), effect estimates will be summarized descriptively by subgroup categories. As the study is not powered for these pre-planned subgroup analyses, no formal hypothesis testing will be done.

Secondary endpoints which may become the basis for additional claims: In case non-inferiority of the primary endpoint is established, these will be evaluated hierarchically.

- 4. Proportion of participants with viral re-suppression (<50 copies/mL) 24 months (16-28 months) after enrollment among all participants with an unsuppressed VL (≥ 50 copies/mL) during the first 12 months of follow-up: This analysis will include individuals with a VL ≥50 copies/mL in the first 12 study months and then directly follow the primary endpoint analysis.
- 5. Proportion of participants with sustained viral suppression (defined as >1 VL <50 copies/mL) during 24 months follow-up: This analysis will directly follow the primary endpoint analysis with endpoint adapted to sustained viral suppression <50 copies/mL throughout the study. Sustained viral suppression is defined as >1 VL <50 copies/mL from study start to end of 24-month window (0-28 months) along with no VL ≥50 copies/mL.

Secondary endpoints indicative of clinical benefit or harm: These will be evaluated independently of the primary objective and without hierarchy / multiplicity adjustment.

- 6. **Rate of mortality at 12 and 24 months after enrollment:** This analysis will use Cox regression adjusted for clinic and district by study arm.
- 7. **Proportion of participants with confirmed TB diagnosis at 12 and 24 months after enrollment:** This analysis will directly follow the primary endpoint analysis with endpoint TB diagnosis (window: 0 months to primary endpoint or 28 months).
- 8. **Disengagement from care at 12 and 24 months after enrollment:** This analysis will directly follow the primary endpoint analysis with endpoint disengagement from care at 24 months, defined as neither a documented visit attendance nor a VL measurement (window: 16-28 months).

Secondary endpoints expressing supportive evidence:

- 9. Time to follow-up VL in case of an unsuppressed VL (≥ 50 copies/mL): This analysis will consider the time in weeks to follow-up VL in case of an unsuppressed VL (≥ 50 copies/mL) as outcome and use a multi-level linear regression model including clinic cluster as a random effect, arm allocation and the randomization stratification factor (district) as a fixed effect.
- 10. Time to ART regimen adaption in case of virologic failure: This analysis will consider the time in weeks to ART regimen adaption in case of virologic failure (defined as two consecutive VLs ≥1'000 copies/mL or three consecutive VLs ≥20 copies/mL from VITAL start 22.12.2022 and two consecutive VLs ≥50 copies/mL from 23.12.2022 − VITAL closure) as outcome and use a multi-level linear regression model including clinic cluster as a random effect, arm allocation and the randomization stratification factor (district) as a fixed effect.
- 11. Rate of clinic visits at 24 months after enrollment: This analysis will consider the number of clinic visits throughout the study period as outcome and use and use a multi-level Poisson regression model with offset study duration including clinic cluster as a random effect, arm allocation and the randomization stratification factor (district) as a fixed effect.
- 12. Proportion of participants with ART regimen modification due to virologic failure at 12 and 24 months among participants with virologic failure: This analysis will only include people with a virologic failure (defined as two consecutive VLs ≥1′000 copies/mL or three consecutive VLs ≥20 copies/mL from VITAL start 22.12.2022 and two consecutive VLs ≥50 copies/mL from 23.12.2022 VITAL closure). Then, this analysis will directly follow the primary endpoint analysis with endpoint ART modification.
- 13. **Proportion of participants having ever received TPT:** This analysis will directly follow the primary endpoint analysis with endpoint having ever received TPT by 24 months.

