1.4. SAP revisions

Version	Date	Justification for each SAP revision	Timing of SAP revision in relation to study
1.1	28.07.2025	- Change in secondary endpoint 13 due to data issues: updated from "having received a course of TPT throughout the study" to "having ever received a course of TPT," as the first TPT measurement was not consistently collected at enrolment, making the baseline estimate unreliable. - Change in sensitivity analysis 2 due to methodological clarification: updated from "multiple imputation" to "imputation," as a single imputation method was used rather than a multiple imputation approach - Change in secondary endpoint analyses: no longer reporting adjusted risk differences for secondary endpoints due to convergence issues. - Clarification: No regression model will be fitted if the number of events per model parameter is below 10, to avoid overfitting and to ensure reliable coefficient estimation.	During analysis

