3.3. Sample size

We calculated the sample size for the non-inferiority cluster randomized design which corresponds to an individually randomized design multiplied by a design effect (3–5). We will use odds ratios (ORs) to assess the effect of the intervention on our binary primary endpoint. An OR of 1 corresponds to no relative effect, an OR >1 to a positive relative and an OR <1 to a negative relative effect in the intervention versus control clusters. We aim at testing the null hypothesis H_0 : OR \leq margin of non-inferiority (NI) versus the alternative hypothesis H_1 : OR > NI, where the rejection of the null hypothesis implies non-inferiority. The NI margin for the OR of reaching our primary endpoint is set to 0.8 (see section 3.4).

We estimated an intraclass correlation coefficient of 0.04 as the proportion of the variance explained by the cluster structure in our population and included the estimated mean cluster size and standard deviation to our design effect. Our desired type I error rate was chosen as 0.025. With 9 clusters in the intervention group and 9 clusters in the control group, we will have 85% power to detect a one-sided difference of >10% in the primary endpoint between the intervention and the control arm.

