3.4. Framework

This is a non-inferiority trial. If non-inferiority of the primary endpoint is established, we will assess superiority.

We chose a NI margin for the odds ratio of reaching our primary endpoint of 0.8, i.e., if the lower bound of the one-sided 97.5% confidence interval for the adjusted odds ratio for the primary outcome exceeds 0.8, then our intervention is non-inferior to standard of care. On an absolute scale, this non-inferiority margin corresponds to a higher absolute probability of failing to reach the primary endpoint of 5% in the intervention compared to the control group, if 65% of participants in the control arm will be engaged in care with documented viral suppression at 24 months follow-up.

If the lower bound of the two-sided 95% confidence interval for the adjusted odds ratio for the primary endpoint exceeds 1.0, we will consider our intervention superior.

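### If the identity-link model fails, the adjusted risk difference and its interval are dropped, although the logistic mixed model already planned can supply both

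*SAP*

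**What the plan says.** SAP section 6.2, General, plans two effect measures: "For the primary outcome and its sensitivity analyses, we will report adjusted odds ratios and adjusted risk differences derived from regression models". The risk difference comes from a model with an identity link, and the section gives one contingency: "If a model fails to converge using the identity link function (for estimating the adjusted risk difference), only adjusted odds ratios will be reported". No other estimator is named.

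The primary-outcome paragraph of section 6.2 specifies a "multi-level logistic regression model including clinic cluster as a random effect, arm allocation and the randomization stratification factor (district) as a fixed effect" and then states, with no condition attached: "Results will be reported as adjusted odds ratios and absolute differences with confidence intervals".

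The revision table in section 1.4, for version 1.1 and with timing given as during analysis, lists: "no longer reporting adjusted risk differences for secondary endpoints due to convergence issues".

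Section 3.3 fixes the margin on the odds-ratio scale: "The NI margin for the OR of reaching our primary endpoint is set to 0.8". Section 3.4 explains that margin as 5 percentage points more failures in the intervention arm, on the condition that 65% of control participants succeed.

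**The concern.** Whether readers receive an adjusted absolute effect depends on whether one optimiser converges. The risk is not hypothetical. The revision table shows that convergence trouble arose in this trial, and that the response was to give up the quantity instead of changing how it is estimated.

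The margin was set as an odds ratio but explained in percentage points, at a single control proportion. If the observed control proportion differs from 65%, readers will want the absolute difference and its confidence interval to see how large a loss the data exclude. An identity-link failure would leave them with an odds-ratio interval and two raw percentages. The logistic mixed model behind the primary test contains everything needed for an adjusted risk difference, so the loss is avoidable.

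**Working it through.** **1. The plan's own figure.** Inputs: margin OR = 0.8 (section 3.3) and control proportion p0 = 0.65 (section 3.4). Formula: p1 = p0·OR / (1 − p0 + p0·OR).

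- At 65%: 0.52 / (0.35 + 0.52) = 0.5977. The difference is 0.65 − 0.5977 = 5.2 points, so the stated 5% reproduces.
- At 70%: 0.56 / 0.86 = 0.6512, difference 4.9 points.
- At 80%: 0.64 / 0.84 = 0.7619, difference 3.8 points.
- At 90%: 0.72 / 0.82 = 0.8780, difference 2.2 points.

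The 5-point explanation is thus tied to the 65% assumption. The other proportions are illustrative; the SAP does not give them.

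**2. What survives an identity-link failure.** Under section 6.2 the adjusted odds ratio with its interval and the raw percentages by arm remain. The adjusted risk difference and its interval do not.

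**3. Can the planned model supply the difference?** For arm a, let risk(a) be the mean over all participants of the integral of expit(b0 + b1·a + b2·district + u) over u ~ N(0, σ²), where u is the clinic effect. The risk difference is risk(1) − risk(0).

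This was tried on simulated trials with these inputs:

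- 18 clinics with the allocation of Table 1 in section 3.2.
- ICC 0.04 (section 3.3), placed on the latent logistic scale: σ² = (0.04/0.96)·π²/3 = 0.137.
- Cluster sizes with mean 200, SD 100 and minimum 30. This is an assumption, because the SAP gives no sizes.
- Maximum likelihood with 25-point quadrature, 200 runs per setting.

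| Control proportion | True OR | True difference (points) | Mean standardised difference | SD across runs | Logistic model converged |
|---|---|---|---|---|---|
| 65% | 0.8 | −5.1 | −4.8 | 4.7 | 100% |
| 85% | 0.8 | −3.0 | −3.0 | 2.6 | 100% |
| 93% | 0.8 | −1.6 | −1.6 | 1.6 | 100% |
| 65% | 1 | 0 | −0.1 | 4.3 | 100% |
| 85% | 1 | 0 | 0.2 | 2.5 | 100% |
| 93% | 1 | 0 | 0.0 | 1.5 | 100% |

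The largest gap, at 65% and OR 0.8, is within one Monte Carlo standard error: 4.7/√200 = 0.3 points. The true value there is 5.1 and not 5.2 because the mixed model's odds ratio is conditional on clinic, while the difference is averaged over clinics.

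**4. How likely is identity-link trouble?** This was not simulated directly. A rough indicator is whether the overall proportion plus three SDs of the clinic proportions reaches 1. It did so in 2.5% and 5% of runs at 65%, 69% and 71% at 85%, and 93% and 95.5% at 93%. These figures depend on the assumed cluster sizes.

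The direction matters for sensitivity analyses 1 and 2. The <1000 copies/mL cutoff keeps every primary success, and imputation can only turn failures into successes. Both proportions are therefore at or above the primary one. The primary analysis could have a risk difference where these two lack it.

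**5. Which interval?** Table 1 gives 5 + 5 clinics in Butha-Buthe and 4 + 4 in Mokhotlong. An uncorrected clinic bootstrap within arm-by-district strata understates between-clinic variance by (n − 1)/n, which is 0.80 for n = 5 and 0.75 for n = 4. Since √0.80 = 0.89 and √0.75 = 0.87, standard errors would be about 11–13% too small. The simulation checked point estimates only, not interval coverage.

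**The case against.** The strongest reply is that nothing confirmatory depends on the risk difference. Sections 3.4 and 6.2 judge both non-inferiority and superiority on the adjusted odds ratio. That stands.

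A reader might infer that no absolute information would be reported at all. The SAP does not support this. Section 6.2 commits to percentages by arm, so the observed control proportion will be known and the odds-ratio bound can be converted to approximate points with the formula above. But that conversion treats the control percentage as known without error and the clinic-conditional odds ratio as marginal. It does not replace the adjusted difference with the confidence interval that section 6.2 promises.

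A reader might also infer that the primary analysis will fail, or has failed, to converge. This is not shown. Section 1.4 speaks of secondary endpoints only and does not name the link; the identity link is inferred from section 6.2. The rough indicator was low at the planned 65%.

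Nor did every secondary endpoint lose an absolute effect. Endpoint 6 uses Cox regression, 9 and 10 linear models in weeks, and 11 a Poisson model. None of these relied on an identity-link binomial model.

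Finally, the conditional rule under General and the unconditional promise for the primary outcome can be read as exception and default. They sit awkwardly together but are not a flat contradiction.

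**Conclusion.** The point holds as one of reporting and interpretation. The SAP makes the adjusted risk difference conditional on a fragile model and plans to omit it on failure, when standardising the planned logistic model would provide it. At stake is the adjusted absolute effect with an interval that respects clustering, for the primary outcome and its sensitivity analyses. For binary secondary endpoints that effect has already been dropped.

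The change from 5.2 points at 65% to 2.2 at 90% should not be read as the size of this defect. It is a property of any odds-ratio margin and would be the same if the risk difference were always reported. It shows only why readers need the absolute estimate. The cost of the omission beyond the reported percentages cannot be quantified from the SAP.

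That the remedy works rests on the simulation's assumed cluster sizes, on the ICC of 0.04 applied on the latent logistic scale, and on the logistic mixed model itself converging in the real data. This is a cheap improvement.

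**What to change.** In section 6.2, replace the identity-link model and the odds-ratio-only fallback with marginal standardisation of the fitted logistic mixed model: predict each participant's risk under both arms, integrate over the clinic random effect, average, and subtract. Name this marginal risk difference as the target.

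Use a delta-method interval with a small-sample t reference based on the 18 clinics. One way to set the degrees of freedom is clinics minus the fixed effects (intercept, arm, district): 18 − 3 = 15. Do not use a clinic bootstrap within arm-by-district strata.

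Apply it to the primary outcome, its three sensitivity analyses, and the binary secondary endpoints that follow the primary analysis, wherever the events-per-parameter rule in section 6.2 allows a model. For endpoints 12 and 13, do so only if a model is reported at all, since section 4.1 limits supportive endpoints to descriptive statistics.

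Record the change in section 1.4 with its date, and disclose that it was made during analysis. It alters no hypothesis test.

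Cost: a few lines of R and some SAP wording, with no new data. The downsides are a change of estimand, from the identity-link coefficient to a marginal difference, and another late amendment.
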